2.6 Analysis of outcomes

2.6.1 Primary analyses

The analysis of these outcomes will be a generalised linear model analysis using generalised estimating equations (GEE) with a log link function, and adjusting for multiple births. The estimate of effect will be a relative risk, with a 95% CI.

Analyses of the disability components will be restricted to those that survived to 24 months. A formal analysis will only be performed if there are adequate event numbers (greater than 10 events) at 24 months in each treatment arm.

Table 7: Outcomes at 24 months corrected age, by treatment

	Outcomes at 24 months	ICC n/N (%)	DCC n/N (%)	Relative risk (95% CI)	p-value
	y outcome: or major disability*				
Second	ary outcomes:				
٠	Death				
٠	Major disability*				
٠	Cerebral palsy ⁺				
•	Severe visual loss ⁺				
٠	Deafness ⁺				
٠	Major problems with language/speecht				
•	Cognitive delay ⁺				
with	ajor disability is one or more of the following: (a language or speech or cognitive delay. ese analyses are restricted to those that were				najor proble

August 2020

Page 9 of 17

Page 73 of 81

APTS FU Statistical Analysis Plan v2.2

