7.9 Clinical Study Report	
7.10 Publication Policy	
8 LIST OF SUB-STUDY APPENDICES	
Appendix 1	
9 REFERENCES	33

SYNOPSIS

Primary clinical hypothesis:

An autologous transfusion of placental blood at birth will improve health outcomes in preterm babies. Placental transfusion by deferred cord clamping is associated with an 8% absolute risk difference, from 30% to 22% in mortality and/or major morbidity, at 36 weeks post menstrual age.

Study objective:

To establish if placental transfusion in preterm babies less than 30 weeks gestation will improve health outcomes compared with the standard practice of early cord clamping.

Study design:

This is a multicentre 2-arm parallel open label randomised controlled trial

Study interventions:

The two arms of the trial comprise:

(a) early cord clamping (which is the control arm)

(b) deferred cord clamping (for 60 seconds or more with the baby held below or at the level of the placenta)

Duration: 48 months for recruitment with a further 24 months for follow-up i.e. total study duration of 72 months.

Study population: babies of 29 ⁶ weeks gestation or less

Primary outcome

Death and/or major morbidity at 36 completed weeks post menstrual age

Secondary outcomes include

Incidence of the following outcomes up to 36 completed weeks post menstrual age unless specified otherwise:

- 1. Death
- 2. Major morbidity
- 3. Death and major morbidity in infants of 27 ° to 29° weeks gestation
- 4. Death and major morbidity in infants of 26 ⁶ weeks gestation or less
- 5. Death or major disability up to 3 years corrected age

Tertiary (hypothesis generating) outcomes include

Birth weight, number of exchange transfusions, number of partial exchange transfusions

Pre-defined subgroups:

- i. Gender
- ii. Age: Infants of 26 ⁶ weeks gestation or less or 27 ⁰ weeks gestation or more
- iii. Caesarean Section vs Vaginal birth

Power and Sample Size

At least 1500 infants and a primary outcome rate in the immediate clamping group of 41.6% will have 80% power to detect a 24% RRR, allowing for 30% non-compliance at 2p = 0.05.

Page 20 of 81

Determine whether deferring cord clamping for 60 seconds or more results in a decrease in mortality and major morbidity at 36 weeks post menstrual age for pre term babies born less than 30 weeks gestation.

[figure not shown]

Figure 1. Australian Placental Transfusion Study schema.

Page 21 of 81

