3.3 Randomisation

Timing of randomisation

While consent can be attained at any time, randomisation should only take place when delivery is considered inevitable, for example when labour is considered irreversible or when the operating theatre is booked for Caesarean Section and the baby's estimated gestation is less than 30 weeks gestation. Randomisation should be performed allowing sufficient time to use the Interactive Voice Response System i.e. at least ten minutes before the expected birth, or longer than this for multiple births.

Method of randomisation

Randomisation can be done by any member of the obstetric, midwifery, or neonatal team using a phone to call a computerised interactive voice response system.

Randomisation will be performed by using an interactive voice response system built by an independent statistician at the NHMRC Clinical Trials Centre, University of Sydney. All data will be stored securely by the statistical group at the centre.

Randomisation will be by the method of minimisation with two strata: Institution and Gestational age (<27 weeks; >=27 weeks). Multiple births will be randomised separately.

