8.2 Statistical Analysis

The analysis population will not include babies that were randomised but stillborn. Additionally, babies that were randomised in anticipation of imminent birth, but were subsequently born after 30 weeks will not be included in the intention to treat population.

The primary analyses will be performed on assigned treatment (intention to treat). Continuous data will be summarised using means for normally distributed variables and medians otherwise. Binary outcomes will be summarised using percentages. Groups will be compared using chi-square tests or t-test where appropriate. Adjusted analyses will use logistic or linear regression where appropriate. Time to event outcomes will be analysed with proportional hazards regression. Safety outcomes may be analysed using a "treatment received" analysis. No adjustments will be made for multiple comparisons.

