2.6.2 Adjusted analyses

An additional analysis will use GEE as described above and will additionally adjust for appropriate baseline characteristics including gestational age (<27 weeks vs \geq 27 weeks), gender, birthweight (into quartiles), multiple birth (singleton vs multiple birth) and mode of delivery (vaginal versus caesarean). This will only be performed for the primary outcome and death by 24 months.

Table 8: Adjusted analyses for outcomes at 24 months corrected age*

Outcomes at 24 months	ICC n/N (%)	DCC n/N (%)	Relative risk (95% CI)	p-value
Primary outcome:				
Death or major disability*				

Death

*Models are adjusted for gestational age (<27 weeks vs \geq 27 weeks), gender, birthweight (into quartiles), multiple birth (singleton vs multiple birth) and mode of delivery (vaginal versus caesarean).

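### The primary GEE leaves out both minimisation factors, so its test is conservative; gestational age belongs in it, and birthweight does not belong in the adjusted effect model

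*Supplement*

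**What the plan says.** Protocol V4.0, section 3.3: "Randomisation will be by the method of minimisation with two strata: Institution and Gestational age (<27 weeks; >=27 weeks"). The same section adds: "Multiple births will be randomised separately".

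SAP v2.2, section 2.6.1, fits a "generalised linear model analysis using generalised estimating equations (GEE) with a log link function, and adjusting for multiple births". On reporting it says: "The estimate of effect will be a relative risk, with a 95% CI". The multiple-birth adjustment can be read as clustering or as a covariate. Neither reading brings in a minimisation factor.

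Section 2.6.2 plans an additional model, for the primary outcome and death only. It adds the gestational-age stratum and "gender, birthweight (into quartiles), multiple birth (singleton vs multiple birth) and mode of delivery (vaginal versus caesarean"), all described as baseline characteristics. Institution is absent from the text and from the Table 8 footnote. The multiple imputation analysis (2.6.4) uses the same covariates in both its imputation and modelling stages. The Cox model for time to death (2.6.5) adjusts for gestational age. Sites enter only through the clusters of the adherence-weighted analysis (2.6.3.2, Table 9).

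The synopsis of protocol V4.0 lists among its tertiary, hypothesis-generating outcomes: "Birth weight, number of exchange transfusions, number of partial exchange transfusions". Section 3.4.5 puts birth weight first.

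**The concern.** Minimising on gestation removes chance imbalance in a factor that strongly predicts death and disability. A model without that factor still counts the imbalance as possible error, so its standard error describes a noisier trial than the one that was run. The cost is power, in a follow-up study planned at 80% after allowing for 30% non-compliance.

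No planned analysis of the primary outcome has both minimisation factors as covariates. The only planned effect models of that outcome with a gestation covariate (2.6.2, and its imputed counterpart in 2.6.4) also contain birthweight. An infant is weighed after the cord is clamped, and the intervention transfers blood volume, so birthweight can carry part of the treatment's effect.

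**Working it through.** **1. The plan's own power figure.** SAP Table 1, first row: N = 1350 (675 per arm), 35% to 25%, 30% non-compliance. Diluting the 10-point difference to 7 points, split evenly, gives 33.5% against 26.5%. Power = Phi[(0.07 - 1.96 x sqrt(2 x 0.30 x 0.70/675)) / sqrt((0.335 x 0.665 + 0.265 x 0.735)/675)] = Phi[(0.07 - 0.0489)/0.0249] = 80.2%. The other five rows come to 79.5-80.1% on the same basis. The table reproduces and is not in question.

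**2. Closed-form check of the standard errors.** Assumed gradient: 60% below 27 weeks and 15% at or above, with one third of infants below. These are the subgroup rates in section 8.1 of the superseded protocol, for a 36-week composite that then included chronic lung disease. They serve only to size the effect. Take 250 + 500 infants per arm (750) and no treatment effect; the overall rate is 30%.

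- SE reported by the unadjusted model: sqrt[2 x 0.70/(750 x 0.30)] = 0.0789.
- True SE with the strata balanced: sqrt[2 x (250 x 0.60 x 0.40 + 500 x 0.15 x 0.85)/(750^2 x 0.30^2)] = 0.0699.
- Actual type I error of the nominal 5% test: 2 x [1 - Phi(1.96 x 0.0789/0.0699)] = 2.7%.
- SE with the stratum in a Poisson model with robust variance: about 0.0699, an interval 11% narrower. A fully efficient log-binomial fit would give 1/sqrt(187.5 + 44.1) = 0.0657, or 17% narrower.

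With 50% and 20%, the unadjusted SE stays 0.0789 and the true SE is 0.0750. Type I error is 3.9%, and the interval narrows by 5% (7% for the efficient fit).

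**3. Power at RR 0.80, with variances at that alternative.** For 60%/15%, the treated rates are 48%/12% (24% overall). The reported unadjusted SE is sqrt[0.70/225 + 0.76/180] = 0.0856 and the true SE is 0.0775. Unadjusted power: Phi[(0.2231 - 1.96 x 0.0856)/0.0775] = 76%. Adjusted: Phi[0.2231/0.0775 - 1.96] = 82%, or 85% with the efficient fit. For 50%/20%, the figures are 75% against 78-79%. The gain is 3-9 points.

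**4. Simulation of minimisation.** N = 1400, 22 sites, 33% below 27 weeks, 1000 trials per row, log-link model with robust SE. Site SD is on the logit scale and is an assumption, as are the gradients. Type I error and SEs are at RR 1. "Both" has gestational age and site in the model. Clustering of multiple births was not simulated.

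| >=27 / <27 weeks | Site SD | True SD of log RR | Mean SE, unadjusted / both | Unadjusted interval wider by | Type I error, unadjusted / both | Power at RR 0.80, unadjusted / both |
|---|---|---|---|---|---|---|
| 27% / 51% | 0 | 0.071 | 0.073 / 0.071 | 3.5% | 4.1% / 5.0% | 80.8% / 81.9% |
| 27% / 51% | 0.4 | 0.069 | 0.072 / 0.069 | 4.9% | 3.7% / 4.6% | 80.4% / 82.1% |
| 22.5% / 60% | 0 | 0.068 | 0.073 / 0.068 | 8.0% | 2.9% / 5.0% | 80.0% / 83.4% |
| 22.5% / 60% | 0.4 | 0.066 | 0.072 / 0.066 | 8.9% | 2.9% / 4.3% | 81.6% / 86.3% |
| 15% / 60% | 0 | 0.072 | 0.082 / 0.073 | 12.8% | 2.1% / 4.7% | 74.3% / 79.5% |
| 15% / 60% | 0.4 | 0.072 | 0.081 / 0.072 | 13.2% | 2.6% / 6.0% | 73.1% / 79.0% |

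Simulation error near 5% is sqrt(0.05 x 0.95/1000) = 0.7 points. Gestational age alone gives 2.8-12.9% of width at RR 1; adding site changes this by 0-2%. At RR 0.80 with both factors, non-coverage was 4.6-6.9%. The 6.9% (steepest gradient, site SD 0.4) is a reason not to fit a separate term for every very small site.

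**5. Birthweight.** The protocol background cites a 47% gain in blood volume in preterm infants from a full transfusion, over half of it by 1 minute. The sub-study background cites blood volumes of about 90 mL/kg. That gives 0.47 x 0.5 x 90 = 21 mL/kg, or about 21 g per kg at an assumed 1 g/mL. Blood received before early clamping and non-compliance would lower the contrast. With an assumed shift of 10-20 g, an SD near 260 g and a 10-20% change in log risk per 100 g, adjusting for quartiles moves a null relative risk to about 1.01-1.03, against an SE near 0.07.

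**The case against.** The strongest reply is that nothing here invalidates the primary result. Omitting balanced factors neither biases the estimate nor inflates type I error, and the order of analyses is consistent across documents. Protocol V4.0, section 8.2, says "Groups will be compared using chi-square tests or t-test where appropriate" and leaves adjustment to regression; the follow-up application treats baseline adjustment as a sensitivity analysis. A gestation-adjusted estimate is already planned for the primary outcome and for death. All of this stands. What remains is which estimate is primary, and that the planned adjusted one omits institution and includes an outcome.

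Three stronger readings are tempting, and the documents do not support them. A reader might take the 17% narrowing as the expected gain. It needs an efficient log-binomial fit and a gradient from a superseded protocol and a composite since redefined. A reader might blame institution equally, but it adds only 0-2% in width. A reader might say that adjustment can never change what is estimated. That holds only if the relative risk is common to both strata: at 60%/15% an inverse-variance fit gives the younger stratum 187.5/231.6 = 81% of the weight, against its 150/225 = 67% share of events.

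Nor can the adjusted estimate be called materially biased by birthweight. The documents give no figure for the intervention's effect on measured weight, and the models concerned are supportive.

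**Conclusion.** The point holds as a matter of efficiency and of consistency with the randomisation. The primary model omits both minimisation factors, so its standard error is too large and its test conservative, though not biased. Over the assumed gradients the unadjusted interval is about 3-13% wider (adjustment narrows it by about 3-12%), type I error is about 2-4%, and adjustment adds 1-6 points of power at RR 0.80 by simulation and 3-9 by formula. The omission is certain from the text. Its size is not, because no 24-month rates by gestation are given. Using birthweight as a covariate is wrong in principle and probably of small effect. The change is worth making; leaving it unmade would not overturn a conclusion.

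**What to change.** - **2.6.1:** add the gestational-age stratum and institution to the log-link GEE, state that clustering is on the mother, and make this the primary estimate. Use institution as randomised and merge only sites too small to fit, for example by the 22-cluster grouping of Table 9. The 15-cluster grouping pools many more sites by geography, which the SAP itself calls arbitrary. If the model does not converge, use Poisson with robust SE. If site terms remain unstable, gestational age alone keeps most of the gain. Keep the present model as supportive.
- **2.7:** state that the common relative risk rests on similar effects in the two gestation strata, which the planned interaction test examines.
- **2.6.2 and the modelling stage of 2.6.4:** drop birthweight and add institution. Birthweight may stay as an auxiliary variable in the imputation stage.

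The cost is SAP wording and a refit of the affected models, with no new data. If unblinded analysis has already been done, report the adjusted estimate beside the planned one and label it post hoc.

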Comparisons between treatment arms on pre-specified endpoints will be undertaken at the two-sided 5% level of significance according to the intention-to-treat analysis principle. Binary endpoints will be analysed by two-sided chi-squared tests. Continuous variables (e.g. ASQ score) will be compared by t-tests or non-parametric equivalent as necessary. Treatment effects adjusted for baseline characteristics will be estimated in a series of sensitivity analyses using a general linear modelling approach. These methods will also be used to identify clinically important prognostic factors and heterogeneity in subgroup analyses. No adjustments will be made for multiple comparisons, but secondary analyses will be interpreted in proper context.

Independent Data and Safety Monitoring Committee:

An Independent Data and Safety Monitoring Committee (IDSMC) is monitoring the progress of all aspects of APTS recruitment and subsequent childhood follow up to ensure that they meet the highest standards of ethics and patient safety. It is also reviewing interim data and other emerging evidence, including relevant RCTs and overviews of RCTs. During the recruitment phase, the IDSMC will advise the TMC if in their view there is proof beyond reasonable doubt of net clinical benefit or harm for all infants, or for a subset of infants, that might be expected to influence the management of many clinicians. Data on study outcomes are being monitored annually, or more often if requested by the IDSMC, to ensure safety and that event rates meet protocol projections.

Feasibility, teamwork and collaboration:

We anticipate no problem in recruiting and following up the planned subjects. Ethics approval and parental consent have been obtained. The CIs and AIs have a strong record of teamwork and collaboration in trials, cohort and follow up studies in Australia, New Zealand and overseas, funded

Page 61 of 81

by NHMRC, NZ HRC, UK MRC, UK DFID, WHO and others, with publications in *New England Journal of Medicine, Lancet*^{4,11,12, 17-20,50,61,62} and other peer-reviewed journals.^{3,6,13,14,23,44,45,48,49,63}

Expected results:

Our hypothesis is that DCC will improve the primary outcome of death or major disability on follow up, with no increase in major disability or in any of its components, including cerebral palsy. DCC will improve the secondary outcomes of (i) mortality and (ii) disability and (iii) ASQ score.

Limitations:

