1 SYNOPSIS

1.1 Primary clinical hypothesis:

An autologous transfusion of placental blood at birth will improve health outcomes in preterm babies born less than 30 weeks.

1.2 Study design:

This is a multicentre 2-arm parallel open label randomised controlled trial

1.3 Study interventions:

The two arms of the trial comprise:

- early cord clamping (which is the control arm) is clamping the cord within 10 secs of birth
- delayed cord clamping (for 60 seconds or more with the baby held below or at the level of the placenta)

1.4 Outcomes for the follow-up study:

Primary outcome Death and/or major disability at 24 months

Secondary outcomes Incidence of the following outcomes at 24 months:

- 1. Death
- 2. Major disability
- 3. Components of major disability
- 4. ASQ domain scores

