2 STATISTICAL ANALYSIS

The primary analyses will be performed on assigned treatment. As randomisation occurs when birth is imminent, occasionally babies are not born immediately following randomisation. Babies that are stillborn or born after 30 weeks gestation are not to be included in the intention to treat population.

As consent for the babies recruited into the pilot APTS study did not include collection of follow-up data, these pilot babies are not included in the APTS FU study (n=35).

P-values less than 0.05 will be considered statistically significant and there will be no adjustments for multiple comparisons.

Page 4 of 17

Page 68 of 81

APTS FU Statistical Analysis Plan v2.2

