2.6.3.2 Weighted subgroups by treatment adherence approach

Additionally, a weighted average approach, weighting by measures of treatment received will be undertaken, following the same principles used in the APTS main study analyses, while preserving the effect of randomisation. In these planned analyses we propose the following two approaches:

(a) sites which enrolled 50 or more babies will be considered a cluster and sites with less than 50 babies will be amalgamated to make a cluster of over 50 with other sites in the same geographic area;

(b) sites which enrolled 10 or more babies will be considered a cluster and amalgamated into a cluster with sites with less than 10 babies will be amalgamated with others in the same geographic area to form another 'cluster' with 10 or more babies (as shown in Table 9).

August 2020

Page 10 of 17

Page 74 of 81

APTS FU Statistical Analysis Plan v2.2

These clusters are slightly different from those proposed in the main paper as we have fewer patients with the follow-up component of APTS (1531 vs 1566), and also fewer with complete data at 2 years. Analysis (b), in which sites of 10 or more babies will be considered a 'cluster' as per Table 9, will allow us to assess the effect of placing less emphasis on the arbitrary grouping of sites by geographical location in analysis (a).

The main measure to be used to estimate treatment adherence will be the mean difference in clamp time (in seconds) between the ICC and DCC arms. Additional measures to be investigated include:

- mean clamp time in seconds in the DCC arm only
- proportion of compliant babies, where compliant is <10 seconds and not milked versus >=60 seconds and not milked
- proportion of babies who are compliant in the DCC arm only (>=60seconds and not milked)

For each measure of treatment adherence, the average for each treatment in each cluster will be calculated. For some measures, the difference between the two treatments will be calculated while for others, the measure of treatment received in the delayed clamping arm alone will be used. This value will then be used to rank the (a) 15 and (b) 22 clusters (as below in Table 9) for increasing adherence to protocol. These clusters in (a) and (b) will be grouped into 3 sets according to adherence to protocol, i.e. (a) 5 'low', 5 'medium' and 5 'good' adherence to protocol treatment (total 15 clusters) or (b) 7 'low', 8 'medium' and 7 'good' adherence to protocol treatment (total 22 clusters).

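### Requiring more than 10 events in each arm denies an uncommon disability component with a lopsided split any relative risk, interval or p-value, while a balanced split with the same total gets all three

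*Supplement*

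**What the plan says.** The follow-up SAP v2.2, section 1.4, lists "Components of major disability" among the secondary outcomes. Section 2.6.1 sets the analysis: a GEE model with a log link that adjusts for multiple births. On the result it says: "The estimate of effect will be a relative risk, with a 95% CI". It then turns to the components: "Analyses of the disability components will be restricted to those that survived to 24 months". The next sentence is the condition at issue: "A formal analysis will only be performed if there are adequate event numbers (greater than 10 events) at 24 months in each treatment arm". Because it directly follows the sentence on components, I read it as applying to them.

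No exact test, total-event criterion or other fallback is given for a component that fails. The shell of Table 7 has a row for each component, with n/N (%) for each arm beside the relative risk and p-value columns. The condition therefore removes the inference and leaves the counts.

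Section 2 of the SAP sets the significance rule: "P-values less than 0.05 will be considered statistically significant and there will be no adjustments for multiple comparisons". The funding application for the childhood follow-up, under its expected results, states a hypothesis about these rows: that deferred clamping will improve the primary outcome "with no increase in major disability or in any of its components, including cerebral palsy".

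**The concern.** A minimum-events rule is meant to avoid fitting a model to too little information. For comparing two arms of similar size, the natural measure of information is the total number of events. This rule instead looks at the smaller of the two arm counts, which depends on the treatment effect as well as on how common the component is. For a given rate in the worse arm, the larger the benefit or harm, the more likely the other arm falls to 10 or fewer and the comparison is dropped.

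At stake are the less common components and the stated hypothesis of no increase in any of them, cerebral palsy included. A clear imbalance would appear as two bare percentages. The components that do receive relative risks would tend to be those with more even splits.

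**Working it through.** **The plan's own figures.** The threshold of 10 has no stated derivation, so there is nothing to reproduce for it. The nearest planning figure is Table 1 in SAP section 1.5: N = 1350, 35% to 25%, 30% non-compliance, 80% power. Diluting the difference by 30% gives 35% − 0.7 × 10% = 28%. A two-sided 5% test of 35% vs 28% with 675 per arm has power 0.791. The six rows of Table 1 give 0.786 to 0.793, all consistent with 80%.

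**Inputs for the check.**
- Condition: at least 11 events in each arm (SAP 2.6.1).
- Follow-up cohort: 1531 babies (SAP 2.6.3.2), allocated about 1:1 (782 vs 784 in the main study, Table 2).
- Assessed survivors per arm: not given. I assume 600 to 700, which means removing 1531 − 1200 = 331 or 1531 − 1400 = 131 for deaths and missing assessments.
- Component rates: not given. I assume 1% to 10% in the higher-rate arm.
- Infants are treated as independent; multiple-birth clustering is ignored.

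**Step 1: splits that need no assumed rate.** Fisher exact p-values, the same to the digits shown at 600 and 700 per arm:

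| Events | Total | Ratio | Fisher p | Analysed? |
|---|---|---|---|---|
| 11 vs 11 | 22 | 1.0 | 1.0 | yes |
| 4 vs 18 | 22 | 4.5 | 0.004 | no |
| 2 vs 20 | 22 | 10 | 0.0001 | no |
| 8 vs 25 | 33 | 3.1 | 0.004 | no |
| 10 vs 40 | 50 | 4.0 | <0.0001 | no |

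The last row has more than twice the events of the first.

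**Step 2: how often the comparison is withheld.** With n per arm, risk p in the higher-rate arm and relative risk RR, let X ~ Bin(n, p) and Y ~ Bin(n, p × RR). Then

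P(withheld) = 1 − P(X > 10) × P(Y > 10).

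Example: n = 700, p = 3%, RR = 0.5. P(X > 10) = 0.994 and P(Y > 10) = 0.480, so P(withheld) = 1 − 0.994 × 0.480 = 0.52. Results for n = 700 and n = 600:

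| Risk, higher-rate arm | RR 1.0 | RR 0.5 | RR 0.33 |
|---|---|---|---|
| 1% | >99% / >99% | >99% / >99% | >99% / >99% |
| 2% | 32% / 57% | 92% / 97% | 99% / >99% |
| 3% | 1% / 6% | 52% / 72% | 91% / 96% |
| 5% | 0% / 0% | 4% / 12% | 39% / 60% |
| 10% | 0% / 0% | 0% / 0% | 0.2% / 1% |

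The labels of the arms can be swapped, so the table serves for harm as well as benefit.

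**Step 3: does it withhold results that would have been informative?** Using a pooled z-test at |z| > 1.96, at 3% and RR 0.5 the test is nominally significant in 48% / 42% of trials (n = 700 / 600). It is both significant and withheld in 38% / 40%, so 79% / 94% of the significant results would not be reported as such. At 5% that share is 5% / 18%, and at 10% about 0%.

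**Step 4: a condition on the total instead.** The smallest total the present rule can pass is 11 + 11 = 22. Requiring a total of at least 22 raises the chance of analysis at 3% and RR 0.5 from 48% / 28% to 97% / 86%. At 2% and RR 0.5 it rises only from 8% / 3% to 44% / 20%, so a total-based condition alone does not serve the rarest components.

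**The case against.** A reader might infer that the rule hides large benefits or harms. Table 7 does not support that: every component has its row with counts, denominators and percentages, and anyone can form a crude ratio from them.

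Nor does the rule act on large effects in general. At about 10% risk it is practically inert even at RR 0.33. At 1% it withholds nearly everything, including null comparisons, which is ordinary sparse-data caution. Some components may well be common: the echocardiography sub-study background cites around 15% moderate to severe developmental disability in survivors, and the funding application assumes a 20% event rate for the Bayley-III calibration.

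The effects illustrated are also large against the plan's own. Table 1 implies 25/35 = 0.71 before dilution and 28/35 = 0.80 after it. At 3% risk, RR 0.80 is withheld in 6% / 17% of trials (n = 700 / 600) and RR 0.71 in 13% / 29%. Finally, a log-link GEE can be unstable with few events, the components are secondary, and death, major disability and their composite have their own rows.

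All of this limits the reach of the point, and I accept it. It does not rescue the form of the rule. Model instability is a reason to change method when an arm is sparse, not to give no estimate. Caution about sparse data cannot explain passing 11 vs 11 and refusing 10 vs 40. Printed counts also do not supply the interval needed to judge whether an increase in a component has been excluded.

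**Conclusion.** The point holds for uncommon components, those at roughly 2% to 5% in the higher-rate arm. There the condition withholds the formal comparison more often the larger the effect: at RR 0.5, about 92–97% of trials at 2% (against 32–57% with no effect), 52–72% at 3% (against 1–6%) and 4–12% at 5%. These figures rest on assumed rates, on 600 to 700 assessed survivors per arm and on independence between infants. The event splits in Step 1 need only the assumed arm size.

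The stronger inference, that the trial's main finding is at risk, is not supported. At the planned 25% to 40% the primary outcome would have hundreds of events and clears the condition easily. This is a should-fix for secondary outcomes. It matters because the funding application names the absence of harm on every component as an expected result.

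**What to change.** Replace the per-arm condition in section 2.6.1 with a rule that every component is reported with a relative risk or risk difference and an exact or score 95% interval beside the counts already in Table 7. An exact or small-sample method should be used when either arm is sparse. If a condition is still wanted before the GEE model is fitted, base it on the total over both arms, for example at least 22. Below that total, the exact or score interval should still be given.

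The cost is one or two sentences in the SAP and a few wide intervals in the table. The exact methods for sparse rows would ignore the clustering of multiple births, and a footnote to Table 7 should say so.
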